The secondary objectives of this study include assessing depression, spirituality, quality of life, perceived self-boundaries, pain and natural killer (NK) cell activity in participants, and examining possible relationships between measures of the psilocybin experience and anxiety and spiritual beliefs.

Depression: We will assess the effects of psilocybin-assisted psychotherapy on symptoms of depression. Changes in depression will be assessed via clinician-administered and self-report instruments at baseline and two weeks after the second psilocybin-assisted session. When applicable, changes in depression will be assessed two weeks after the second open-label session and two months after the second open label or experimental session.

Quality of Life, Beliefs about Spirituality and Self-Boundaries: We will investigate the effects of psilocybin-assisted psychotherapy on beliefs about life purpose, spirituality, self-boundary and quality of life. Changes in spiritual beliefs and quality of life will be assessed via self-report measures at baseline and two weeks after the second psilocybin session. When applicable, changes in spiritual

beliefs and quality of life will be assessed two weeks after the second open-label session and two months after the second open label or experimental session.

Pain: A third secondary objective is to learn whether psilocybin-assisted psychotherapy produces at least transient changes, as analgesia or reduction in physical pain. Changes in pain will be assessed via daily diaries using visual analog scales and via daily diaries of medication use. When applicable, changes in pain will be assessed two weeks after the second open-label session and on the day two months after the second open label or experimental session.

Immune function: We wish to investigate the short-term and continued effects of psilocybin-assisted therapy on immune system function. Changes in immunological function will be assessed by NK cell counts made at baseline, 24 hours after each experimental session and two weeks after the second psilocybin-assisted session. When applicable, NK cell counts will occur 24 hours after each open-label session and two weeks after the second open-label session.

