The sponsor or the investigator (following consultation with the sponsor) has the right to discontinue this study at any time. If the trial is prematurely terminated, the investigator is to promptly inform the study subjects and she or he should assure appropriate therapy and follow-up. If the trial or study is prematurely discontinued, all procedures and requirements pertaining to the archiving of the documents will be observed. All other study materials will be returned to the sponsor, will be treated in accordance with federal and local regulations. DEA requires destruction of unused schedule 1 drugs in studies.

Data Analysis

The primary analyses for this study will be a repeated measures analysis of variance (ANOVA) with condition (active placebo versus experimental dose) as a between-subject

factor and time of administration (baseline versus two weeks after the second experimental psilocybin-assisted session) as a repeated measure. The investigators will employ separate repeated measures ANOVAs to examine the effects of psilocybin-assisted psychotherapy on all outcome variables, including the primary outcome variable. Separate analyses will be performed for HADS, HAM-A and STAI anxiety scores, HADS and HAM-D depression scores, EORTC-QLQ-C15 scores, FACIT-Sp scores and NK cell counts. The investigators will perform post-hoc tests (as Tukey's test) on any statistically significant interactions. Probability of rejecting the null hypothesis will be set at 0.05. Because of the pilot nature of this study and small sample size, we will not employ Bonferroni corrections for when examining analyses results for measures of anxiety. In the case of pain levels measured by daily diary, the investigators will perform two repeated measures ANOVAs comparing average pain levels at baseline versus average pain levels for the weeks immediately after the first and after the second experimental sessions, with p. set at 0.05. The investigators are interested in discovering whether there are differences in pain level between active placebo and experimental dose participants immediately after undergoing psilocybin-assisted psychotherapy.

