
what significance these changes in gene expression have on the generation of subjective effects.

Table 1

Psilocybin Binding Data

Receptor	Ki (nM)	Hot Ligand	Species	Source	Reference
5HT1A	190	3H-8-OH-DPAT			
5HT2A	6	3H-DOI	Rat/cow	Brain	(McKenna et al. 1990)
5HT2C	410	3H-Ketanserin	Rat/cow	Brain	(McKenna et al. 1990)

Table 2

Psilocin binding Data

Receptor	Ki (nM)	Hot Ligand	Species	Source	Reference
5-HT1A	49	3H-8-OH-DPAT	Human	Cloned	(Blair et al. 2000)
5-HT2A	25	125I-DOI	Rat or bovine	Cloned	(Blair et al. 2000)
5-HT2C	10	125I-DOI	Rat	Cloned	(Blair et al. 2000)

Some neuroscientists hypothesize that serotonin 5HT_{1A} and 5HT_{2C} receptors play a role in producing at least some and perhaps most of the effects of serotonergic hallucinogens (Nichols 2004). It is notable that most 5HT_{2A} agonists also act on 5HT_{2C} receptors, making it difficult to single out only one of the two receptors as key for producing the effects of psychedelics. To date, work has not specifically studied the effects of psilocybin or psilocin on 5HT_{2C} receptors. Psilocybin activates 5HT_{1A} receptors. Direct application of psilocybin to dorsal raphe nucleus (DRN) neurons reduces firing of DRN neurons (Aghajanian et al. 1968; Aghajanian and Hailgler 1975), an effect attributed to 5HT_{1A} activity. Administering the 5HT_{2A/2C} antagonist ketanserin along with psilocybin reduced most psychedelic effects in humans without reducing self-reported fatigue or inattention, and without preventing psilocybin from altering binocular rivalry (Carter et al. 2005b), findings suggesting that 5HT_{1A} receptor activation may produce or modulate some, but not all, psilocybin effects.

Previous research has reported that LSD produced analgesia that outlasted its subjective effects (Kast 1966). It is possible that psilocybin shares this effect with the related serotonergic hallucinogen. The pharmacological mechanisms for LSD-induced analgesia remain unclear, and researchers do not know if psilocybin produces analgesia. If LSD causes analgesia as a result of activating 5HT₂ or 5HT_{1A} receptors, then psilocybin may share these effects as well.

Secondary Pharmacology

Safety Pharmacology

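### Pain is recorded daily and the objective covers a transient effect, but the diary analysis averages each whole post-session week, so an effect of one or two days would be largely averaged away

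*Protocol*

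**What the plan says.** In the protocol, *Secondary Objectives* (Pain) sets out to "learn whether psilocybin-assisted psychotherapy produces at least transient changes, as analgesia or reduction in physical pain". On measurement it states: "Changes in pain will be assessed via daily diaries using visual analog scales and via daily diaries of medication use". The *Time and Events* table shows the pain diary running from Visit 3 to Visit 10. Appendix A describes a 10-cm line scored 0 to 10, and the diary form in Appendix B asks how much pain was felt that day.

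*Data Analysis* then fixes the test: two repeated measures ANOVAs at 0.05, described as "comparing average pain levels at baseline versus average pain levels for the weeks immediately after the first and after the second experimental sessions". The next sentence gives the interest as "differences in pain level between active placebo and experimental dose participants immediately after undergoing psilocybin-assisted psychotherapy". No day-level or shorter post-session summary of the diary is described. Pain is otherwise tested by a t-test at two months. It is also covered indirectly through the EORTC-QLQ-C15, which has a pain scale and is compared between baseline and two weeks after the second session.

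On rationale, *Drug Activity Related to Proposed Action* says: "Previous research has reported that LSD produced analgesia that outlasted its subjective effects". It adds that analgesia from psilocybin is not established. No duration in hours or days is given.

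**The concern.** The shortest effect that the objective admits is the one the chosen summary shows least well. The acute effects of psilocybin last about four to six hours (*Disease History and Related Research*), and the analgesia hypothesised by analogy with LSD need only outlast them. If it lasts a day or two, five or six unaffected days enter the same average. The days that carry the signal are recorded but never examined separately.

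What is at stake is mainly description. In a nine-person pilot the value of the pain data lies in showing whether there is a pattern worth pursuing. A weekly mean can make a clear short-lived fall look like almost nothing, in the estimate as well as in the p-value.

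**Working it through.** **The plan's own figure.** *Statistical Power* gives 0.1143 for a two-sample t-test, 6 against 3, effect size 0.6. With noncentrality 0.6/√(1/6 + 1/3) = 0.6/0.7071 = 0.849, 7 degrees of freedom and two-sided 0.05, the noncentral t gives 0.1143. It reproduces. It concerns efficacy in general; the protocol gives no effect size, SD, duration or power for pain.

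**Raw dilution.** Assume a constant fall of δ points on k days of the seven, zero on the rest, and all affected days inside the averaged week. The weekly mean shifts by δ·k/7. For δ = 2 (an illustrative value):

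| Days of effect k | Share kept k/7 | Shift in weekly mean |
|---|---|---|
| 1 | 14% | 2 × 1/7 = 0.29 |
| 2 | 29% | 2 × 2/7 = 0.57 |
| 3 | 43% | 2 × 3/7 = 0.86 |
| 5 | 71% | 2 × 5/7 = 1.43 |
| 7 | 100% | 2.00 |

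**Gradual decay instead.** With half-life h days and r = 0.5^(1/h), the weekly mean keeps (1 + r + … + r⁶)/7 of the day-1 effect: 28%, 44%, 56% and 76% for h = 1, 2, 3 and 7.

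**Allowing for noise.** A longer mean is less noisy, so the standardised loss can be smaller than the raw loss. Assume a between-person SD of change s_b and a day-to-day SD s_w, each 1 to 2 points. The SD of an m-day mean change is then √(s_b² + s_w²/m).

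Two-day effect, two-day window against weekly mean. The ratio of standardised differences is (7/2)·√[(s_b² + s_w²/7)/(s_b² + s_w²/2)]:
- s_b = 1, s_w = 2: 3.5 × √(1.571/3) = 2.53
- s_b = 2, s_w = 1: 3.5 × √(4.143/4.5) = 3.36

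Two-day effect, three-day window (one unaffected day included). The ratio is (7/3)·√[(s_b² + s_w²/7)/(s_b² + s_w²/3)]:
- s_b = 1, s_w = 2: 2.333 × √(1.571/2.333) = 1.91
- s_b = 2, s_w = 1: 2.333 × √(4.143/4.333) = 2.28

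If the effect lasts all seven days, only the square-root terms remain. The two-day mean then keeps 72% to 96% of the weekly mean's standardised effect, and the three-day mean 82% to 98%.

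**Power, 6 against 3.** For a 2-point, two-day effect over s_b and s_w in {1, 1.5, 2}, by the same noncentral t:
- weekly mean: 6% to 10%
- two-day mean: 17% to 51%, below 40% in eight of the nine combinations
- three-day mean: 11% to 29%

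**The case against.** Four points weigh against a stronger reading.

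- **Duration is unknown.** Nothing in the protocol makes one or two days likelier than a week, and the objective's wording sets a floor that also admits lasting change. The raw loss runs from 86% at one day to none at seven. This stands: the figures are conditional. But an unknown duration is a reason to have a short-window summary beside the weekly one, not a reason to have the weekly one alone.
- **A reader might infer that the analysis contradicts the stated interest in pain immediately after treatment.** The text does not support that. *Data Analysis* itself applies the word to the weeks following each session, and the event it refers to is psilocybin-assisted psychotherapy, not the moment of dosing. A week also fits the 7-to-14-day gap between sessions.
- **A reader might infer that a null pain result would be due to the window.** That goes too far. With nine participants, a real two-day effect would usually miss significance even in a well-matched window, and *Statistical Power* says openly that power is very low.
- **A short window can be misplaced.** The capsule is given at about 10:00 AM and the diary asks about that day, so analgesia that outlasts the acute effects by some hours first appears in the session-day entry. A window starting the day after would miss it.

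It can also be said that supplementary windows and plots belong in an SAP, which is not shown. That is fair for the plots. The weekly window, however, is fixed in the protocol itself.

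**Conclusion.** The point holds as a weak choice of summary for one part of a secondary objective. Under a constant effect that then stops, the seven-day mean keeps 14% to 29% of the raw size of an effect lasting one or two days. The duration is an assumption, and for a week-long effect there is no dilution. The complementary loss of 71% to 86% is on the raw scale and should not be read as a loss of power or of standardised effect; those depend on SDs that the protocol does not give.

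Nor do the figures support replacing the weekly mean. If the effect persists, the weekly mean is the better summary, so substitution would be a trade-off. Adding a short window is a cheap improvement that lets the trial address the transient part of its own objective.

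**What to change.** In *Data Analysis*, keep the two weekly-mean ANOVAs and label them the test of persisting change in pain. State whether the session-day entry belongs to the week.

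Add one pre-specified short-window comparison for each session: the mean of the session-day entry and the next one or two daily entries (choose the number in advance), minus the participant's mean diary score before Visit 5, compared between arms. Report the arm difference with a confidence interval, not as a significance test. Plot daily mean pain by arm, and show pain-medication use on the same days from the medication diary, so that a fall in pain can be read alongside any change in analgesic use.

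The cost is protocol wording and some additional analysis of data already collected, with no new visits or measurements. The short-window mean is noisier than a weekly one. The session-day entry also covers hours before dosing, which the daily plot helps the reader to judge. One more uncorrected secondary comparison is added.

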The active placebo in this study will be a low dose of the investigational drug. Active placebo dose of psilocybin was chosen on the basis of early and recent studies of psilocybin in humans (Hasler et al. 2004; Isbell 1959; Moreno et al. 2006; Passie et al. 2002). This dose was chosen for its ability to produce a few of the effects of psilocybin without producing any of the potentially therapeutic effects. People may perceive lights or colors as being brighter and sounds as being different, and they may experience slight changes in mood, cognition or perception. A 4 mg dose of psilocybin is not expected to generate a mystical or transformative experience.

Sample Population and Subjects

The study will enroll nine (9) individuals with the following criteria listed below. Study drop-outs or withdrawals will be replaced until nine participants have completed the randomized phase of the study. Study completion will be defined as attending visits from screening up through the follow-up two weeks after the second psilocybin-assisted session. Participants who are unable to complete or withdraw from the open-label phase or before the two-month follow-up phase will not be replaced. Inclusion Criteria

Inclusion Criteria

Prospective participants must meet the following inclusion criteria listed below to be eligible for study enrollment.

1. Have been diagnosed with Stage IV melanoma with a life expectancy of one year or less
2. Meet diagnostic criteria for anxiety on the SCID, or a score of 8 or higher on the HADS Anxiety score.
3. Diagnosis must be a new diagnosis of anxiety subsequent to diagnosis with melanoma.
4. Are 18 years or older,
5. Live with another adult who is their primary caregiver, who can also provide transportation to and from the cancer center for each experimental session and who also consents to take part in a parallel investigation of anxiety and depression in primary caregivers. The same caregiver may remain overnight with participants after each psilocybin session.
6. Have a Mini-Mental State Exam score of 27 or higher.
7. Are willing to commit to medication dosing, experimental sessions with overnight stay, traveling to follow-up sessions, and to complete the evaluation instruments.
8. Are willing to refrain from taking any anti-depressants during the study period.
9. Are willing to refrain from taking any benzodiazepines during the 24 hours preceding each scheduled psilocybin, placebo, or open label session.

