All outcome measures selected for this study were chosen because they are well-recognized in the literature and because they are or will be used in related pilot studies, allowing comparison across these investigations. The primary outcome measure for this study will be the HADS anxiety score. The investigators will also measure anxiety with the STAI and the HAM-A. The investigators will assess depression with HADS depression scores and with the HAM-D. Participant beliefs about life purpose and spirituality will be measured with the FACIT-Sp, spirituality in relation to self-concept by the SELF, and quality of life will be assessed with the EORTC-QLQ-C15. Daily pain levels will be assessed via participant response on a visual analog scale, and daily pain and anxiety medication use will serve as an indirect measure of anxiety and experienced pain. Natural killer cell counts will serve as a measure of innate immune system function.

All participants will be screened via SCID and HADS, as described above in “Screening”. The investigators will also use MMSE scores to assess study eligibility and mental competence throughout the course of the study.

The SCQ will serve as a process measure, assessing presence and degree of effects of psilocybin, and the SELF will serve as a process measure of self-boundary change. The KRPS, a measure frequently employed in studies of people with cancer, will serve as a means of rating performance status.

Table 1: List of assessments for use in this study. Time listed in minutes.

Assessment	Abbreviation	Measure of	Time needed	Clinician rated	Participant Self-rated	Purpose of Assessment/Measure
Daily Medication Diary	--	Anxiolytic & pain management meds	5 min		X	Outcome
Daily Pain Level Diary	--	Daily pain levels	5 min.		X	Outcome
Europ. Organiz. For Research and Treatment of Cancer; Quality of Life Questionnaire-C15	EORTC QLQ-C15	Global quality of life	5-10 minutes.		X	Outcome
Functional Assessment of Chronic Illness Therapy-spirituality	FACIT-Sp	Spiritual or life purpose beliefs	5 min.		X	Outcome
Hamilton Anxiety Rating Scale	HAM-A	Anxiety	5-10 min	X		Outcome
Hamilton Depression Rating Scale	HAM-D	Depression	5-10 min	X		Outcome
Hospital Anxiety and Depression Scale#	HADS	Anxiety + Depression	5-10 min.		X	Screening & Outcome
Karnofsky Performance R__ Scale	KPRS	Everyday life function	5 minutes	X		Supplemental
Mini Mental State Examination	MMSE	Mental status / competency	15 minutes	X		Screening, continued eligibility

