After giving written consent, participants will be screened for presence of anxiety and for the presence of any psychiatric conditions that preclude study participation, such as psychosis. The principal investigator will conduct the screening evaluation in his office. The Structured Diagnostic Clinical Interview (SCID) will be used for diagnosing anxiety and detecting any conditions that preclude study participation, and the Mini Mental State Evaluation (MMSE) will be used to determine mental state and competency to take part in the study. Only participants with MMSE scores of 27 or higher will be eligible for study participation. The Hospital Anxiety and Depression Scale (HADS) will be used to quantify anxiety. Only people who are diagnosed with anxiety via SCID or who have a HADS Anxiety score of eight (8) or higher will be eligible for study participation. Once it is determined that participants meet study eligibility criteria, participants will complete or undergo additional assessments of anxiety and depression, quality of life and functional status, described above. The primary caregivers will complete the HADS. The investigators will also provide participants with daily pain and medication diaries and instructions on how to complete them. Participants will begin completing daily pain and medication diaries starting after baseline analysis.

Randomized blinded Study phase

Randomization

Upon enrollment into the study, participants will be assigned to one of two conditions, active placebo (4 mg psilocybin) or full experimental intervention (25 mg psilocybin). Active placebo in this study is a low dose of the investigational drug that will not produce the unique effects of psilocybin. Participants have a 66% chance of assignment to the full experimental intervention, with six of nine participants will be assigned to receive the full experimental intervention and three will be assigned to receive active placebo. The internal review committee coordinator at the study site will generate and maintain the randomization code and procedure. Condition assignment will be maintained from study enrollment up through the course of the study, as there is no crossover design. If there is an adverse event or other emergency requiring knowledge of participant's condition assignment, as when pharmacological intervention is necessary, the blind may be broken for an individual participant.

Introductory Psychotherapy Session (Visits #4 and #4.5)

Psychotherapy

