Introductory psychotherapy sessions will be recorded to audio and video. No identifying information save assigned participant subject number will be written on any session recordings. Participants will have an opportunity to review session recordings.

Assessment

Participants will undergo assessment with MMSE to ensure their continued eligibility prior to each introductory psychotherapy session. They will complete the HADS and STAI prior to the first introductory session, and the FACIT-SP and EORTC-QLQ-C15 prior to the second introductory session. They will complete daily pain and medication diaries during this time period.

Psilocybin-Assisted Psychotherapy (Visit #5, Visit #8)

Psychotherapy

There will be two psilocybin-assisted psychotherapy sessions scheduled to occur seven to fourteen (14) days apart, on study visits #5 and #8. Both psilocybin-assisted psychotherapy sessions will take place at the study site and will be staffed by the two investigator-therapists, one male and one female. Procedures for the two drug-assisted sessions will be identical. During the second experimental session, the participant and therapist-investigators may discuss material or experiences from the first psilocybin-assisted session.

Participants will arrive at the Cancer Center at approximately 9:00 AM. Participants will be instructed to refrain from alcoholic beverages starting 12:00 on the night prior to each psilocybin-assisted session, and to eat only a light breakfast on the morning of the

session. On arrival, they will have a blood draw for the assessment of liver function and metabolism, and they will have urinary drug and pregnancy screens. After undergoing these screens, one of the investigators will conduct the MMSE, and the participant will complete outcome measures. He or she may return completed daily pain and medication diaries at this point. Results from laboratory tests will be available approximately 45 minutes after the blood draw, and significantly abnormal results will result in rescheduling of psilocybin session or withdrawing the subject from the study. Positive pregnancy screen will result in withdrawal from the study.

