If at least four participants complete measures during the follow-up two months after the second experimental or open-label psilocybin-assisted therapy session, then the investigators will perform separate repeated-measures ANOVAs on the anxiety, depression, quality of life and spirituality scores listed above, with p. set at 0.05. The investigators are chiefly interested in differences between baseline and two-month follow-up scores. If a sufficient number of participants complete pain measures on the date of the two-month follow-up session, then the investigators will perform a t-test to compare VAS pain ratings on the day of the two-month follow-up with the average pre-psilocybin pain rating.

Given that only three participants will be eligible for the open-label phase of the study, the investigators do not plan to perform formal comparisons between anxiety, depression, spirituality or quality of life across the randomized and open-label study phases. However, the investigators will perform informal observations and present descriptive statistics for all outcome variables two weeks after the second open-label psilocybin-assisted session.

Before analyzing differences between degree of mystical experiences or changes in spiritual identity for active placebo and experimental dose participants, the investigators will first perform a matched-sample t test to determine whether there were significant differences between mystical experience (SCQ) and self-concept boundary/spiritual identity (SELF) scores measured after each of the two psilocybin-assisted sessions. If there are no significant differences between SCQ and SELF scores after the first and the second psilocybin session, then the investigators will compute the average between the two scores and employ the average SCQ and SELF score in nearly all subsequent analyses of these scores. Subsequent analyses will include an analysis of variance comparing SCQ and SELF scores in active placebo and full-dose participants, and correlational analyses of anxiety (HADS and STAI) and depression (HADS) scores as related to SCQ and SELF scores, with p. set at 0.05. The investigators may also compare

SCQ scores and NK cell counts made from blood sampled approximately 23 hours after each psilocybin-assisted session to see whether there are associations between presence and degree of mystical experience changes in immunological function.

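### The two-month change from baseline in HADS anxiety starts from a score that is also an entry criterion, so regression to the mean can show a fall that no assured comparator removes

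*Protocol*

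**What the plan says.** Inclusion criterion 2 admits people who "Meet diagnostic criteria for anxiety on the SCID, or a score of 8 or higher on the HADS Anxiety score". The Screening and Baseline evaluation section repeats that people "who have a HADS Anxiety score of eight (8) or higher will be eligible for study participation", with a SCID diagnosis as the alternative route. Assessments and Measures says "The primary outcome measure for this study will be the HADS anxiety score", and Table 1 there lists HADS for both screening and outcome.

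The Time and Events table marks HADS once at Visit 3, the visit that also carries the baseline evaluation and enrolment. The Visit by Visit Description likewise has one HADS there. The qualifying score is therefore also the baseline score. At Visit 4, the next visit, participants give another: "They will complete the HADS and STAI prior to the first introductory session".

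The two-month analysis in Data Analysis is conditional: "If at least four participants complete measures during the follow-up two months after the second experimental or open-label psilocybin-assisted therapy session". Separate repeated-measures ANOVAs then follow, "with p. set at 0.05", and the stated interest is "The investigators are chiefly interested in differences between baseline and two-month follow-up scores". Participants on 4 mg who enter the open-label phase are measured two months after their second open-label 25 mg session. For that phase the Visit by Visit Description takes the Visit 10 assessments as baseline in most cases.

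**The concern.** A person admitted because one HADS reading was high is expected to read lower next time, whatever happens in between. In the randomised two-week comparison both arms were selected alike, so the fall is shared and cancels in expectation. The two-month contrast of interest is change within persons. Nothing removes the fall there, because the 4 mg group may by then have received 25 mg.

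The bias points towards apparent lasting benefit on the primary outcome measure. The Rationale section says the pilot data will inform whether to start Phase 3 studies and with which drug and dosing schedule, so a durability signal partly produced by the entry rule could mislead that decision.

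**Working it through.** **The plan's own figure.** The plan gives no error rate for the two-month test. Its computed figures are power values. The 6-versus-3 value of 0.1143 is reproduced by a two-sided t-test at 0.05 with 7 df and noncentrality 0.6 × √(6×3/9) = 0.849. It concerns the between-group comparison and does not bear on this point.

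**Inputs from the protocol.** Entry cut 8; alpha 0.05 (two-sided assumed); at least four completers; at most nine, since "The study will enroll nine (9) individuals with the following criteria listed below".

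**Assumed inputs.** The protocol gives no HADS mean, SD or retest correlation. Assumed are SD 4, a source mean (before selection) of 7 or 9, correlation r of 0.5 to 0.8, no true change, and normal scores rounded to whole points within 0–21. Unless stated, everyone enters by HADS.

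**Step 1: expected fall.** With a = (7.5 − mean)/SD, where 7.5 is the cut before rounding:

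fall = (1 − r) × SD × φ(a)/[1 − Φ(a)]

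- Mean 7: a = 0.125; 4 × 0.3958/0.4503 = 3.52. Fall = 1.76, 1.05 and 0.70 points at r = 0.5, 0.7 and 0.8.
- Mean 9: a = −0.375; 4 × 0.3719/0.6462 = 2.30. Fall = 1.15, 0.69 and 0.46 points.

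**Step 2: rejection rate with no true change.** Simulated paired t-test, which equals the time effect of a two-occasion repeated-measures ANOVA:

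| Source mean | r | 4 completers | 6 | 9 |
|---|---|---|---|---|
| 7 | 0.5 | 10% | 16% | 25% |
| 7 | 0.7 | 8% | 11% | 16% |
| 7 | 0.8 | 6–7% | 9% | 12% |
| 9 | 0.5 | 7% | 9% | 13% |
| 9 | 0.7 | 6% | 8% | 10% |
| 9 | 0.8 | 5% | 7% | 8% |

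The 6–7% cell depends on how the rare samples with identical differences are counted. Nearly all the excess rejections are falls in anxiety. Over source means 6 to 11 the range is about 5% to 34%.

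**Step 3: entry by SCID.** Suppose a share of the source population qualifies whatever its HADS score (mean 8, r = 0.5). With four, six and nine completers the test rejects in 9%, 12% and 18% if that share is zero, and in 6%, 7% and 9% if it is 30%. It rejects in 5–6% if the share is 60%, and in 5% if everyone qualifies that way.

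**Step 4: condition kept in the model.** In a 6-versus-3 mixed ANOVA at mean 7, the time effect still rejects in 22%, 14% and 11% at r = 0.5, 0.7 and 0.8. The condition-by-time interaction stays near 5%.

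**Step 5: Visit 4 as baseline.** The remaining fall is (r between Visits 3 and 4 − r between Visit 3 and follow-up) × 3.52 at mean 7.

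- Equal correlations: no remaining fall, and rejection of about 5%.
- Correlations 0.8 and 0.5: 0.3 × 3.52 = 1.05 points. Rejection is about 6–7%, 8% and 11% with four, six and nine completers, against 10%, 16% and 25% from Visit 3 at r = 0.5.

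**The case against.** A reader might infer that the two-month test simply has an error rate of 12–25%. The documents do not support that. Those figures need nine completers, a source mean of 7 and entry by HADS alone. Planned Duration calls two-month attendance after the open-label phase very improbable, people lost before that visit are not replaced, and the analysis may run on four. Four to six completers is the more plausible number.

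The SCID route also matters. Inclusion criterion 3 speaks of a new anxiety diagnosis, so many participants may enter by diagnosis, which brings the error close to 5%. This limits the size. It does not remove the point, because the protocol does not restrict entry on HADS alone.

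It can be said that Data Analysis never drops condition from the two-month model, so calling the comparison uncontrolled is an inference. That is fair as a reading of the text. Keeping condition does not rescue the time contrast (Step 4), and after crossover the interaction no longer compares 25 mg with 4 mg.

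Two further inferences fail. The randomised two-week comparison is not biased by this. Nor does a Visit 4 baseline guarantee 5%: Visit 4 falls at about day 7 and follow-up at about day 89 or 132, so adjacent visits may well correlate more closely.

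Finally, baseline definitions are often left to an analysis plan. Here, however, the protocol itself fixes the entry rule, the single Visit 3 reading, the contrast and the 0.05 level.

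**Conclusion.** The concern holds in this limited form. For participants admitted on HADS, the two-month change from Visit 3 is biased towards a fall in anxiety, and the test exceeds its nominal 5%. The direction follows from the design, but the size does not.

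Under SD 4, r of 0.5 to 0.8 and entry by HADS only, the error is about 6–16% with four to six completers and 12–25% with nine at source mean 7. At source mean 9 it is about 5–9% and 8–13%. It is close to 5% if most enter by SCID. This affects a conditional secondary analysis in a nine-person pilot, but one on the primary outcome measure, and it is cheap to improve.

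**What to change.** In the two-month paragraph of Data Analysis:

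- Use the Visit 4 HADS as baseline for the two-month HADS comparison. It is collected before the first introductory session and is not used for selection. Show the Visit 3 result alongside it.
- Describe the comparison as uncontrolled and open to regression to the mean.
- Leave STAI, HAM-A and HAM-D on Visit 3. None is an entry criterion, and the HAM scales are not given at Visit 4.
- State whether participants who entered the open-label phase use their pre-treatment baseline or Visit 10.

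The cost is a few sentences, with no new data collection. The downside is that HADS then has a different baseline visit at two months than at two weeks. The bias is reduced but not certainly removed: about 6–11% rejection remains at source mean 7 if Visits 3 and 4 correlate 0.8 with each other and 0.5 with follow-up.
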